3.4.3. Other outcomes

3.4.3.a. Other UUI/OAB outcomes

i. Bladder diary – We will assess the change in IE frequency and type, number of urgency episodes, urgency severity with voids, number of diurnal voids, and number of nocturnal voids and compare these variables between groups at 6 months and 1 year.

ii. Overactive Bladder treatment satisfaction (OAB-SAT-q)⁵⁸-The OAB-SAT-q is an 11 item instrument designed to assess patient satisfaction with treatment in a clinical setting. There are three 3-item subscales (Satisfaction, Side Effects, Endorsement) and two single items (Convenience, Preference). Response options are presented on 4-, 5-, and 6-point Likert scales. It has demonstrated good psychometric properties in OAB/UUI patients receiving anticholinergic and anticholinergic + behavioral therapies. We will compare change from baseline in OAB-SAT-q scores at 6 months and 1 year between treatment groups.

iii. Overactive Bladder Questionnaire-Symptom subscale (OAB-q) – The OAB-q is a validated, responsive questionnaire that includes 8 symptom bother items (SS) and 25 health related quality of life (HRQOL) items of 4 subscales (coping, concern, sleep, and social interaction).⁵⁵ In a systematic review of UI questionnaires by Avery et al, the OAB-q was rated as “grade A”, highest recommendation specifically for OAB symptoms.⁵⁹ Each item is rated on a 6-point Likert scale ranging from “not at all bothered” to “a very great deal bothered” for symptom items and “none of the time” to “all of the time” for HRQOL items. Subscales are summed and transformed into scores ranging from 0-100 with higher bother scores indicating increasing symptom bother and higher HRQOL scores indicating better quality of life.^{60,61} We will compare change from baseline in OAB-q scores at 6 months and 1 year between treatment groups.

3.4.3.b. Time to failure

For analyzing time to failure, “failure” will be defined as initiation of any additional treatment for either SUI or UUI/OAB symptoms during the follow-up period. Subjects lost to follow up will be censored at the time of their last visit.

3.4.3.c. Quality of life/global impression

We will compare change from baseline in the scores below at 6 months and 1 year between treatment groups.

- a) Incontinence Impact Questionnaire (IIQ)
- b) Pelvic Organ Prolapse/Urinary Incontinence Sexual Questionnaire (PISQ)⁶²
- c) European Quality of Life-5 Dimensions (EQ-5D)⁶³
- d) Adaptation Index

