9 EFFICACY ANALYSES

9.1 Overview of Efficacy Analyses Methods

- All efficacy analyses will be performed on the ITT population.
- All efficacy variables will be summarized by treatment group at baseline and at the 3, 6, and 12-month time points. N, mean, standard deviation, minimum, and maximum will summarize continuous efficacy variables, whereas number and percent will summarize categorical efficacy variables.
- Unless otherwise noted, all analyses of dichotomous outcomes, measured at respective endpoints, will be performed using a generalized linear mixed model. Models will be adjusted for stratification by clinical site and UUI severity group. If there are not enough patients in every clinical site to include the variable in the models as a fixed effect,

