Change from Baseline OAB-q HRQL Coping Score at 12 Months	Continuous	
The OAB-q HRQL Coping Score will be computed at baseline and 12 months (and 3 and 6 months) using the standard scoring algorithm. Specifically, instructions are to sum responses across questions 9, 11, 16, 21, 22, 26, 32, and 33 (1= Not at all, 2=A little bit, 3=Somewhat, 4=Quite a bit, 5=A great deal, 6=A very great deal), then subtract from the maximum possible score (48) and divide by the range of possible score (48-8=40), then multiply by 100. If less than half of the responses are missing, then the score will be calculated by substituting the missing responses with the average of the non-missing responses, otherwise no score is calculated. The outcome will then be computed as the difference in score at 12 months (and 3 and 6 months) and the score at baseline. If data for an assessment time point are missing, the outcome variable will be coded as missing.

Network

Protocol ESTEEM Statistical Analysis Plan

Variable	Type	Definition
Change from Baseline OAB-q HRQL Concern Score at 12 Months	Continuous	The OAB-q HRQL Concern Score will be computed at baseline and 12 months (and 3 and 6 months) using the standard scoring algorithm. Specifically, instructions are to sum responses across questions 12, 13, 14, 19, 23, 25, and 29 (1= Not at all, 2=A little bit, 3=Somewhat, 4=Quite a bit, 5=A great deal, 6=A very great deal), then subtract from the maximum possible score (35) and divide by the range of possible score (42-7=35), then multiply by 100. If less than half of the responses are missing, then the score will be calculated by substituting the missing responses with the average of the non-missing responses, otherwise no score is calculated. The outcome will then be computed as the difference in score at 12 months (and 3 and 6 months) and the score at baseline. If data for an assessment time point are missing, the outcome variable will be coded as missing.

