Change from Baseline OAB-q HRQL Sleep Score at 12 Months	Continuous	The OAB-q HRQL Sleep Score will be computed at baseline and 12 months (and 3 and 6 months) using the standard scoring algorithm. Specifically, instructions are to sum responses across questions 10, 15, 17, 24, and 30 (1= Not at all, 2=A little bit, 3=Somewhat, 4=Quite a bit, 5=A great deal, 6=A very great deal), then subtract from the maximum possible score (30) and divide by the range of possible score (30-5=25), then multiply by 100. If less than half of the responses are missing, then the score will be calculated by substituting the missing responses with the average of the non-missing responses, otherwise no score is calculated. The outcome will then be computed as the difference in score at 12 months (and 3 and 6 months) and the score at baseline. If data for an assessment time point are missing, the outcome variable will be coded as missing.
Change from Baseline OAB-q HRQL Social Score at 12 Months	Continuous	The OAB-q HRQL Social Score will be computed at baseline and 12 months (and 3 and 6 months) using the standard scoring algorithm. Specifically, instructions are to sum responses across questions 18, 20, 27, 28, and 31 (1= Not at all, 2=A little bit, 3=Somewhat, 4=Quite a bit, 5=A great deal, 6=A very great deal), then subtract from the maximum possible score (30) and divide by the range of possible score (30-5=25), then multiply by 100. If less than half of the responses are missing, then the score will be calculated by substituting the missing responses with the average of the non-missing responses, otherwise no score is calculated. The outcome will then be computed as the difference in score at 12 months (and 3 and 6 months) and the score at baseline. If data for an assessment time point are missing, the outcome variable will be coded as missing.

Network

Protocol ESTEEM Statistical Analysis Plan

Variable	Type	Definition

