Change from Baseline OAB-q HRQL Total Score at 12 Months	Continuous	The OAB-q HRQL Total Score will be computed at baseline and 12 months (and 3 and 6 months) using the standard scoring algorithm. Specifically, instructions are to sum the OAB-q HRQL Coping, Concern, Sleep, and Social prior to subtracting from the respective maximum possible scores, then subtract from the maximum possible sum score (150) and divide by the range of possible scores $((18+42+30+10=150)-(8+7+5+5=25)=125)$, then multiply by 100. The outcome will then be computed as the difference in score at 12 months (and 3 and 6 months) and the score at baseline. If any of the subscales are missing, the Total score will also be set to missing. If data for an assessment time point are missing, the outcome variable will be coded as missing.
OAB-SAT-q Satisfaction Score at 12 Months	Continuous	The OAB-SAT-q Satisfaction Score will be computed at 12 months (and 3 and 6 months) using the standard scoring algorithm. Specifically, instructions are to sum responses across questions 1, 2, and 3 (1=Extremely Dissatisfied, ..., 6=Extremely Satisfied), then subtract from the maximum possible sum score (18) and divide by the range of possible scores $(18-3=15)$, then multiply by 100. If less than half of the responses are missing, then the score will be calculated by substituting the missing responses with the average of the non-missing responses, otherwise no score is calculated. If data for an assessment time point are missing, the outcome variable will be coded as missing.

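### The OAB-q Concern row subtracts from 35 although its own range uses 42; if coded as written, reported Concern levels are 20 points too low, while change scores and the HRQL Total are unaffected.

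*SAP*

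**What the plan says.** The table in SAP section 9.2 gives a scoring rule for each OAB-q scale. For Concern the analyst is to "sum responses across questions 12, 13, 14, 19, 23, 25, and 29", with each item coded "1= Not at all, 2=A little bit, 3=Somewhat, 4=Quite a bit, 5=A great deal, 6=A very great deal", and "then subtract from the maximum possible score (35) and divide by the range of possible score (42-7=35"; the result is multiplied by 100. If fewer than half of the items are missing, each missing item takes the mean of the answered items. The analysis variable is the change of this score from baseline, listed under the exploratory outcomes.

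The neighbouring rows follow the same pattern:
- Coping (eight items): "then subtract from the maximum possible score (48) and divide by the range of possible score (48-8=40".
- Sleep (five items): "then subtract from the maximum possible score (30) and divide by the range of possible score (30-5=25". Social, also five items, has the same constants.
- HRQL Total: built from the raw subscale sums, before any subscale subtraction, with the constants printed as "18+42+30+10=150)-(8+7+5+5=25)=125".

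Protocol section 3.4.3.a sets the intended scale: "Subscales are summed and transformed into scores ranging from 0-100", with higher HRQOL scores meaning better quality of life.

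On reporting, SAP section 9.1 states: "All efficacy variables will be summarized by treatment group at baseline and at the 3, 6, and 12-month time points". It lists the mean, SD, minimum and maximum among the statistics for continuous variables. SAP section 8.3 also includes the baseline levels of the QOL measures among the baseline characteristics.

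**The concern.** The Concern sentence uses two different maxima. Its denominator takes 42 as the top of the raw scale, while its numerator subtracts from 35. Only one can be the maximum of seven items coded 1 to 6. The value 35 equals the range, which suggests that the range was entered where the maximum belongs.

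This is an operative scoring instruction, so an analyst who follows it literally produces scores on the wrong scale. Coping, Sleep and Social would sit on 0 to 100 in the same table while Concern did not. Because higher is better on these subscales, Concern would look worse than it is, at baseline and afterwards, in both arms. An analysis of change scores would not reveal the error.

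**Working it through.** **Inputs (SAP section 9.2, Concern row).** Seven items (12, 13, 14, 19, 23, 25, 29), each coded 1 to 6. Stated maximum 35; stated range 42 - 7 = 35.

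**Step 1: reproduce the stated constants.**
- Raw minimum: 7 x 1 = 7.
- Raw maximum: 7 x 6 = 42.
- Range: 42 - 7 = 35.

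The stated range reproduces; the stated maximum does not.

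**Step 2: compare with the other subscales.**

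| Subscale | Items | Items x 6 | Stated maximum | Score range as written |
|---|---|---|---|---|
| Coping | 8 | 48 | 48 | 0 to 100 |
| Concern | 7 | 42 | 35 | -20 to 80 |
| Sleep | 5 | 30 | 30 | 0 to 100 |
| Social | 5 | 30 | 30 | 0 to 100 |

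Concern is the only exception.

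**Step 3: evaluate the formula at its limits.** Let S be the raw sum.
- As written, 100 x (35 - S)/35. S = 7 gives 80; S = 42 gives -20.
- With 42, 100 x (42 - S)/35. S = 7 gives 100; S = 42 gives 0.

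The gap is 100 x (42 - 35)/35 = 20 points for every S. As written, the score is negative for S from 36 to 42.

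**Step 4: missing items.** Substitution changes S but not the constants, so the gap stays at 20. Example: five items answered with sum 20 have mean 4, so the completed sum is 20 + 2 x 4 = 28. As written the score is 100 x (35 - 28)/35 = 20; with 42 it is 100 x (42 - 28)/35 = 40.

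**Step 5: change from baseline.** Let S0 be the baseline sum and S12 the 12-month sum. As written, the change is

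100 x (35 - S12)/35 - 100 x (35 - S0)/35 = 100 x (S0 - S12)/35.

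The 35 in the numerator cancels. With 42 the result is the same, so the change and any between-group comparison of it are identical.

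**Step 6: spread.** Subtracting 20 from every value leaves the SD unchanged. The mean, minimum and maximum each fall by 20.

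**Step 7: HRQL Total.** This row uses raw sums, so the subscale formula does not enter it, and its Concern component is 42. The stated maximum of 150 equals 48 + 42 + 30 + 30. The addends as printed, 18 + 42 + 30 + 10, give 100. The minimum, 8 + 7 + 5 + 5 = 25, and the range, 150 - 25 = 125, are correct.

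**Step 8: look for a correction elsewhere.** The scoring revision in SAP section 9.5.1 concerns the OAB-SAT-q. Section 13 and the SAP's version summaries do not mention Concern scoring.

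**The case against.** The strongest reply is that this is a typing slip without consequence. The row refers to the standard scoring algorithm, the correct 42 stands in the same sentence and again in the Total row, and the protocol fixes the scale at 0 to 100. A programmer may well have coded 42. Even if 35 was coded, the analysed variable is a change score, the outcome is exploratory, and a negative minimum or a ceiling of 80 would show up in the planned summaries.

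Most of this stands. The documents do not show the code, so the effect is conditional, and no planned treatment comparison depends on the constant. What does not follow is that the text can be left alone. Section 8.3 calls for baseline levels. Under section 9.1, a baseline summary can only be of the level, since no change score exists at baseline. Those are planned outputs that a literal reading would misstate. The SAP itself treats scale violations as worth repairing: section 9.5.1 rewrites OAB-SAT-q Endorsement scoring because a missing item could give 109.09. The Concern formula shifts every score and can leave 0 to 100 with complete data.

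A reader might infer three stronger things, none of which the documents support:
- **That every reported statistic is wrong.** The SD is not affected.
- **That the threshold work in SAP section 9.5.6 would misclassify women.** That section names the OAB-q but not the Concern subscale. A cut-off derived from scores that are all shifted by the same amount puts the same women on each side. Only its numerical label would be 20 points too low, which matters when someone applies it to correctly scored data.
- **That the error passes into the HRQL Total.** The Total is built from raw sums.

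**Conclusion.** The Concern scoring rule is wrong as written: the maximum should be 42, not 35. This is certain from the SAP's own item list and coding.

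The effect on results assumes that 35 was programmed literally and used at every visit. In that case Concern levels are exactly 20 points too low and lie between -20 and 80. The reported mean, minimum and maximum levels are wrong by that amount, and a published Concern cut-off would be mislabelled by it. The SD, the change from baseline, the treatment comparison and the HRQL Total are unaffected, as are the primary and secondary UDI outcomes. If 42 was programmed, the defect is confined to the SAP text. Either way the correction is worth making, because the sentence can be coded in two ways and the change scores will not show which was used.

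**What to change.** 1. In the Concern row of SAP section 9.2, replace the maximum of 35 with 42. The range of 35 stays.
2. Confirm in the code that a raw sum of 7 gives 100 and a raw sum of 42 gives 0, and that all programmed Concern scores lie within 0 to 100.
3. In the same edit, check the addends in the HRQL Total row against the source file. The stated 150 requires 48 + 42 + 30 + 30; the printed 18 and 10 may be typing errors or may come from reading the PDF.

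The cost is one number in the SAP, a check of one line of code and a look at the adjacent row. If 35 turns out to have been programmed, the tables of Concern levels need to be rerun; the change-score analyses do not.

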OAB-SAT-q Side Effects Score at 12 Months	Continuous	The OAB-SAT-q Side Effects Score will be computed at 12 months (and 3 and 6 months) using the standard scoring algorithm. Specifically, if the response to question 5 is Never then the score is 100, regardless of the responses to questions 6 and 7. If the response to question 5 is not Never, then sum the responses across questions 5 (reverse coded: 1=All of the time, ..., 5=A little of the time), 6 (1=Extremely bothersome, ..., 5=Not at all bothersome), and 7 (1=A great deal, ..., 7=Not at all), then subtract from the maximum possible sum score (15) and divide by the range of possible scores $(15-3=12)$, then multiply by 100. If less than half of the responses are missing, then the score will be calculated by substituting the missing responses with the average of the non-missing responses, otherwise no score is calculated. If data for an assessment time point are missing, the outcome variable will be coded as missing.

Network

Protocol ESTEEM Statistical Analysis Plan

Variable	Type	Definition
OAB-SAT-q Endorsement Score at 12 Months	Continuous	
The OAB-SAT-q Endorsement Score will be computed at 12 months (and 3 and 6 months) using the standard scoring algorithm. Specifically, instructions are to sum responses across questions 9 (1=Definitely would not use the same treatment again, ..., 4=Definitely would use the same treatment again), 10 (1=Definitely would not recommend, ..., 4=Definitely would recommend), and 11 (1=Extremely Dissatisfied, ..., 6=Extremely Satisfied), then subtract from the maximum possible sum score (14) and divide by the range of possible scores (14-3=11), then multiply by 100. If less than half of the responses are missing, then the score will be calculated by substituting the missing responses with the average of the non-missing responses, otherwise no score is calculated. If data for an assessment time point are missing, the outcome variable will be coded as missing.

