OAB-SAT-q Convenience Score at 12 Months	Continuous	
The OAB-SAT-q Convenience Score will be computed at 12 months (and 3 and 6 months) using the standard scoring algorithm. Specifically, instructions are to use the response to question 4 (1=Extremely Inconvenient, ..., 6=Extremely Convenient), then subtract from the maximum possible sum score (6) and divide by the range of possible scores (6-1=5), then multiply by 100. If the response to question 4 is missing then no score is calculated. If data for an assessment time point are missing, the outcome variable will be coded as missing.

OAB-SAT-q Preference Indicator at 12 Months	Dichotomous	
The OAB-SAT-q Preference Score will be computed at 12 months (and 3 and 6 months) using the standard scoring algorithm. Specifically, the indicator is set to 1 if the response to question 8 is either “Slight preference for the treatment I am receiving now” or “Definitely prefer the treatment I am receiving now”, otherwise it is set to 0. If the response to question 8 is missing then indicator is calculated. If data for an assessment time point are missing, the outcome variable will be coded as missing.
 
The score is calculated as the percentage of participants with Indicator=1 among all non-missing Indicators.

Network

Protocol ESTEEM Statistical Analysis Plan

Variable	Type	Definition
Retreatment at 12 months	Categorical and Dichotomous	
The types of retreatment for SUI or UUI will be identified and categorized from the Additional Therapy and Concomitant Medications forms. Further details can be found in Attachment 16.1.
 
An indicator of retreatment will be calculated for each subject where subjects with retreatment identified above will be assigned “Yes”, otherwise subjects are assigned “No”. The rate of retreatment is calculated as the percentage of participants with indicator=“Yes” among all non-missing indicators.

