The scoring manual for the OAB-SAT-q states that higher scores should correspond to better outcomes and also details that final composite scores for each dimension should be obtained by subtracting raw scores from the highest possible score and dividing by range. However, based on the direction of score for individual responses, this derivation would result in lower scores corresponding with better outcomes. We have adjusting the scoring algorithm instead to be: $100 * (\text{raw score} - \text{lowest possible score}) / \text{score range}$. This calculation results in higher scores corresponding to better outcomes and an overall scale of 0-100.

Additionally, it was observed that the scoring of the OAB-SAT-q Endorsement subscale could have unintended behavior when dealing with missing data. The range of possible responses for component questions 9 and 10 (1 through 4) is different from the range of possible responses for component question 11 (1 through 6), so if any question is missing, the range of possible values for the imputed value of the missing response does not match the range of the original question. For example, if $Q9=4$, $Q10=\text{Missing}$, and $Q11=6$, then the imputed value for $Q10$ is 5, which is outside of the 1-4 range possible for $Q10$. This further causes problems when transforming the score as the transformed score can exceed 100. From the example provided, the transformed score is $100 * (\text{sum}(4,5,6) - 3) / 11 = 109.09$.

We have adjusted the missing value handling instead to be: average the non-missing responses as proportions of their maximum possible values (divide each non-missing response by its maximum possible value) and then scaling that average against the maximum possible value of the missing response. For example, if $Q9=4$, $Q10=\text{Missing}$, and $Q11=6$, then the imputed value for question 10 is as follows $[(4/4 + 6/6)/2] * 4 = 4$ and the transformed Endorsement score is $100 * (\text{sum}(4,4,6) - 3) / 11 = 100$, so the score does not exceed 100.

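### The SAP 9.2 table still prints OAB-SAT-q scoring that 9.5.1 replaces, and its Side Effects row codes item 7 up to 7 against a maximum and range that fit only a 1–5 item

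*SAP*

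**What the plan says.** **Definition table (SAP 9.2).** Satisfaction items are coded so that a higher answer is better (6 = extremely satisfied). The row then says "then subtract from the maximum possible sum score (18) and divide by the range of possible scores", that is, 18 − raw over 15. Endorsement (14 − raw over 11) and Convenience (6 − raw over 5) follow the same pattern.

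**Side Effects row (SAP 9.2).** A woman who reports no side effects gets a fixed value: "if the response to question 5 is Never then the score is 100, regardless of the responses to questions 6 and 7". Otherwise three items are summed:
- item "5 (reverse coded: 1=All of the time, ..., 5=A little of the time"
- item "6 (1=Extremely bothersome, ..., 5=Not at all bothersome"
- item "7 (1=A great deal, ..., 7=Not at all), then subtract from the maximum possible sum score (15"

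The row gives the range as 15 − 3 = 12.

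**Later text (SAP 9.5.1).** On the maximum-minus-raw method taken from the scoring manual, this section says "this derivation would result in lower scores corresponding with better outcomes". It substitutes 100 × (raw − lowest)/range and states that the result runs from 0 to 100 with higher scores better. It also replaces the missing-item rule for Endorsement. The version 2.1 change summary lists the revised instructions under 9.5.1.

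**Response formats (Protocol 3.4.3.a).** For the whole instrument: "Response options are presented on 4-, 5-, and 6-point Likert scales".

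**Preference row (SAP 9.2).** "If the response to question 8 is missing then indicator is calculated". The sentence before it sets every response other than a preference for the current treatment to 0. The row later takes the percentage over non-missing indicators.

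**The concern.** A variable-definition table is what a programmer normally works from. Here, four of its rows carry a rule that another section of the same SAP rejects, and nothing in those rows sends the reader to 9.5.1. The same SAP revision added the dryness endpoints to 9.2, so the table was open for editing when the OAB-SAT-q rule changed.

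If the table were followed, a group difference in satisfaction, endorsement or convenience would be reported with the wrong sign. Side Effects would suffer more than a reversal. The value for women without side effects is fixed at 100, while the formula also sends the worst experience to 100. The two ends of the scale would share one value, and flipping the score afterwards could not separate them.

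The item 7 coding is a second, independent fault. It disagrees with the maximum and range in its own row and with the protocol's list of response formats, and 9.5.1 leaves it as it stands. Section 9.5.1 does treat an out-of-range Endorsement score as something to repair, so by the SAP's own standard a Side Effects score outside 0–100 would not be acceptable either.

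**Working it through.** **Reproducing the SAP's own figures.** The Endorsement examples in 9.5.1 check: 100 × (4+5+6 − 3)/11 = 109.09 under the old missing-item rule, and 100 × (4+4+6 − 3)/11 = 100 under the new one.

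**Direction.** For Satisfaction:
- 9.2 gives 100 × (18 − raw)/15 = 100 − 100 × (raw − 3)/15
- 9.5.1 gives 100 × (raw − 3)/15

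Each 9.2 score is therefore 100 minus the 9.5.1 score. Answers 6,6,6 (sum 18) score 0 under 9.2 and 100 under 9.5.1. The same identity holds for Endorsement (14, 3, 11) and Convenience (6, 1, 5): the best answers score 0 under 9.2 and 100 under 9.5.1.

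**Side Effects maximum.** From the printed item codings:
- items 5 and 6 run 1–5 and item 7 runs 1–7, so the minimum sum is 3 and the maximum is 5 + 5 + 7 = 17, range 14
- the row states maximum 15 and range 12, which are not reproduced
- with item 7 coded 1–5, the maximum is 5 + 5 + 5 = 15 and the range 12, which reproduces both

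**Side Effects scores** when item 5 is not 'Never', using the printed 15 and 12:

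| Items 5, 6, 7 | Sum | 9.2: 100 × (15 − sum)/12 | 9.5.1: 100 × (sum − 3)/12 |
|---|---|---|---|
| 1, 1, 1 (worst) | 3 | 100 (same as 'Never') | 0 |
| 3, 3, 3 | 9 | 50 | 50 |
| 5, 5, 5 | 15 | 0 | 100 |
| 4, 4, 7 | 15 | 0 | 100 (same as 'Never') |
| 5, 5, 7 | 17 | −16.7 | 116.7 |

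The first three rows need no seventh option; the last two do. With item 7 at 1–7 there are 5 × 5 × 7 = 175 complete answer patterns. Four of them have sums above 15 (5,5,7; 5,5,6; 5,4,7; 4,5,7) and fall outside 0–100 under either rule. With item 6 missing, item 5 = 5 and item 7 = 7, mean substitution imputes 6. The sum is then 18, which scores 125 under 9.5.1 and −25 under 9.2. With item 7 at 1–5 there are 125 patterns and none is out of range.

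**If seven options were real.** The constants would be 17 and 14: 100 × (17 − 3)/14 = 100.

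**Preference.** No arithmetic applies. The Convenience row just above says that no score is produced when its single item is missing. The Preference row has the same construction without the negative, and then summarises over non-missing indicators. That summary makes sense only if a missing answer produces no indicator.

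**The case against.** The strongest reply is that the SAP has already settled the direction. Section 9.5.1 names the reversal, says its formula is used instead, applies it to every dimension, and is recorded as a version 2.1 change. The 9.2 rows describe their rule as the standard algorithm, so they can be read as reporting the manual from which 9.5.1 then departs. This stands. A reader might infer that the plan leaves the direction open, or that the satisfaction comparison will be reported with the wrong sign. The documents do not support either; the reversal occurs only if someone codes from the outdated table.

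The second reply is that the printed 7 is a one-character slip. The maximum and range in the same sentence fit three 1–5 items, and the protocol lists no 7-point format. This is probably right. It also means that an answer of 7 may be impossible, so scores of 116.7 or −16.7 should not be presented as something the trial will produce. The reply does not remove the inconsistency. The questionnaire is not in the documents, and nothing in the SAP corrects the coding.

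Third, a reader might take the Preference row to count a missing answer as no preference. The row's own wording on missing data and non-missing indicators points the other way, so this is a dropped word and not a scoring policy.

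**Conclusion.** The point holds as a documentation fault in exploratory outcomes.

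- Four rows of SAP 9.2 print a rule that 9.5.1 rejects. Followed literally, they turn x into 100 − x on Satisfaction, Endorsement and Convenience, and give 1,1,1 on Side Effects the same 100 as 'Never'. This depends on 9.5.1 being overlooked.
- The Side Effects row is internally inconsistent as written: 17 and 14 from the printed coding against a stated 15 and 12. No section corrects it. Scores leave 0–100 only if the form has a seventh option, and then for 4 of the 175 complete answer patterns.
- The Preference row lacks a negative that its context supplies.

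It would be wrong to infer a threat to the trial's main conclusions. The OAB-SAT-q appears under exploratory outcomes in SAP 9.2 and exploratory aims in Protocol 6.2.3. The UDI total and subscale analyses and the sample size do not use it. The correction is still worth making, because it is specific and cheap and the rows as printed are wrong by the SAP's own account.

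**What to change.** 1. In SAP 9.2, put 100 × (raw − lowest)/range in the Satisfaction, Side Effects, Endorsement and Convenience rows, or at least refer each row to 9.5.1.
2. In the Endorsement row, replace the plain averaging of missing items with the proportional rule from 9.5.1.
3. Check Side Effects item 7 against the administered form and make coding, maximum and range agree: 1–5 with 15 and 12, or 1–7 with 17 and 14.
4. In the Preference row, restore the negative so that a missing question 8 yields no indicator.
5. If scoring programs already exist, confirm which rule and which item 7 coding they used, and rescore from the item responses if necessary.

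The cost is edits to five table rows, one look at the questionnaire and a short program check. No new data are needed.
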